6. GENERAL ANALYSIS DEFINITIONS

6.1 TREATMENT(S)

For treatment specifications, see Section 4 of CTP.

The following trial periods will be defined: screening, post-randomisation, blinded treatment period (with sub-periods off-treatment, post-treatment and follow-up), open-label treatment period (with sub-periods off-treatment, post-treatment and follow-up) and post-study as follows:

Note: Post-treatment reflects the residual effect period.

Note: the last day of each of the following periods is excluded.

- Screening: from informed consent to randomisation
- Post-randomisation (optional): from randomisation to first randomised trial drug intake in blinded treatment period
- Blinded treatment period: from first randomised trial drug intake (or re-start of treatment if interruption) to last randomised trial drug intake (or the day before start date of interruption, if interruption) plus one day
 - Blinded off-treatment (optional): from start date of interruption to re-start of blinded treatment
 - Blinded post-treatment (optional)^[a]: from the last blinded trial drug intake plus one day to last blinded trial drug intake plus 28 days plus one day or day of first open-label treatment administration (whichever occurs earlier)
 - Blinded follow-up (optional): from last blinded trial drug intake plus 29 days up to the beginning of post-study period. This period is only created if last blinded trial drug intake took place more than 28 days before trial completion, or for patients having prematurely discontinued the blinded treatment and still continuing the trial
- Open-label treatment period: from first open label nintedanib intake (or re-start of treatment if interruption) to last open label nintedanib intake (or the day before start date of interruption, if interruption) plus one day
 - Open-label off-treatment (optional): from start date of interruption to re-start of open-label treatment
 - Open-label post-treatment (optional)^[a]: from the last open-label trial drug intake plus one day to last open-label trial drug intake plus 28 days plus one day
 - Open-label follow-up (optional): from last open-label trial drug intake plus 29 days up to the beginning of post-study period. This period is only created if

last open-label trial drug intake took place more than 28 days before trial completion, or for patients having prematurely discontinued the open-label treatment and still continuing the trial

- Post-study: from the latest of

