 - last trial drug intake plus 29 days
 - date of trial completion
 - follow-up visit
 - early end of treatment visit plus 1 day to database lock

^[a] In addition, a post-treatment period of 7 days will be used for adverse event analyses to more closely reflect the period of time after the last trial drug intake when measurable drug levels or pharmacodynamic effects are still likely to be present.

In addition to the above periods, the following additional period is defined:

- Overall: Combines all available data from Blinded treatment period and Open-label treatment period.

For safety analyses, data up to the end of the blinded / open-label post-treatment period will be considered on-treatment. For on-treatment efficacy analyses, data up to the day after last trial drug intake (included) will be considered.

For efficacy analyses patients will be assigned to the treatment group they were randomised to, for safety analyses patients will be assigned to the treatment group they were treated in.

Details are provided in [Table 6.1: 1](#).

Table 6.1: 1 Summary of analysed periods according to the type of endpoint

Analysed endpoint	Studied period	
	Start date	End date ^{1/1}
For primary analysis (rate of change (slope) in blood CRPM from baseline to week 12)	Baseline (see Section 6.7)	Visit 5 (after time windowing, refer to Section 6.7) Data up to the day after last blinded trial drug intake (included).
For the key secondary endpoint (Proportion of patients with disease progression as defined by absolute FVC (% predicted) decline $\geq 10\%$ or death until week 52)	Main analysis: Baseline (see Section 6.7) Sensitivity analysis: Visit 5 (start of open label treatment)	Visit 10 (after time windowing, refer to Section 6.7) Data up to the day after last open-label trial drug intake (included).
For secondary endpoints (rate of change (slope) in blood C1M and C3M from baseline to week 12)	Baseline (see Section 6.7)	Visit 5 (after time windowing, refer to Section 6.7) Data up to the day after last blinded trial drug intake (included).
For efficacy endpoints from week 12 to week 52 (open-label period)	Visit 5 (start of open label treatment) Note: Covariates can be measured before Visit 5.	Visit 10 (after time windowing, refer to Section 6.7) Data up to the day after last trial open-label drug intake (included).

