For efficacy endpoints from baseline to week 12 (blinded period)	Baseline (see Section 6.7)	Visit 5 (after time windowing, refer to Section 6.7) Data up to the day after last blinded trial drug intake (included).

Table 6.1: 1 (continued) Summary of analysed periods according to the type of endpoint

	Studied period	
Analysed endpoint	Start date	End date^[1]
Rates of decline during blinded period	Baseline (see section 6.7)	Visit 5 (after time windowing, refer to Section 6.7) Data up to the day after last blinded trial drug intake (included).

Table 6.1: 1 (continued) Summary of analysed periods according to the type of endpoint

Analysed endpoint	Studied period	
	Start date	End date ^[1]
Rates of decline during open-label period	Visit 5 (start of open label treatment) Note: Covariates can be measured before Visit 5.	Visit 10 (after time windowing, refer to Section 6.7) Data up to the day after last trial open-label drug intake (included).

Table 6.1: 1 (continued) Summary of analysed periods according to the type of endpoint

	Studied period	
Analysed endpoint	Start date	End date^[1]
AEs and laboratory data		
On-treatment period safety (AEs, laboratory data, including enzymes elevation) during blinded treatment period	Date of first trial drug intake	First day of documented intake of open-label treatment or last blinded trial drug intake plus 28 days or end of treatment, whichever occurs first
	Off-treatment periods not excluded. However, for safety listings, anything happening during a treatment interruption will be flagged as occurring during the off-treatment period (even if between [last trial drug intake; last trial blinded drug intake + 28 days])	
On-treatment period safety (AEs, laboratory data, including enzymes elevation) during open label treatment period	First day of documented intake of open-label treatment	Last open label drug intake plus 28 days or end of treatment, whichever occurs first
	Off-treatment periods not excluded. However, for safety listings, anything happening during a treatment interruption will be flagged as occurring during the off-treatment period (even if between [last trial drug intake; last trial open label drug intake + 28 days])	
On-treatment period safety (AEs, laboratory data, including enzymes elevation) during overall treatment period	Date of first trial drug intake	Last drug intake plus 28 days or end of treatment, whichever occurs first

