	Off-treatment periods not excluded. However, for safety listings, anything happening during a treatment interruption will be flagged as occurring during the off-treatment period (even if between [last trial drug intake; last trial drug intake + 28 days])	

Table 6.1: 1 (continued) Summary of analysed periods according to the type of endpoint

Analysed endpoint	Studied period	
	Start date	End date ^[1]
On-treatment period safety: Liver enzyme and bilirubin elevation between periods (i.e.: the elevation of bilirubin appears within 30 days of the elevation of AST and/or ALT, but in different period)	Date of first trial drug intake	Last open label drug intake plus 28 days or end of treatment, whichever occurs first
	Off-treatment periods not excluded. However, for safety listings, anything happening during a treatment interruption will be flagged as occurring during the off-treatment period (even if between [last trial drug intake; last trial open label drug intake + 28 days])	

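### Four safety rows of SAP Table 6.1:1 cap the on-treatment window at an undefined end of treatment; under the protocol's usage of that term the cap conflicts with the 28-day residual window

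*SAP*

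**What the plan says.** The text of SAP 6.1 sets one rule for all safety data: "data up to the end of the blinded / open-label post-treatment period will be considered on-treatment". It defines the open-label post-treatment period as running "from the last open-label trial drug intake plus one day to last open-label trial drug intake plus 28 days plus one day". The blinded one ends at "last blinded trial drug intake plus 28 days plus one day or day of first open-label treatment administration (whichever occurs earlier". Neither definition mentions end of treatment. SAP 7.8.1 and protocol 5.3.7 and 7.3.4 apply the same 28-day residual effect period to adverse events. SAP 7.8.1 also plans a repeat of the adverse event analysis limited to 7 days after last intake.

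SAP 6.1 then refers the reader to Table 6.1:1 for details. Its four safety rows end as follows:

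- Blinded: "First day of documented intake of open-label treatment or last blinded trial drug intake plus 28 days or end of treatment, whichever occurs first".
- Open-label: "Last open label drug intake plus 28 days or end of treatment, whichever occurs first".
- Overall: "Last drug intake plus 28 days or end of treatment, whichever occurs first".
- Between-period liver enzyme and bilirubin: the same words as the open-label row.

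The note inside the overall row still refers to the full residual window ("even if between [last trial drug intake; last trial drug intake + 28 days"), and the other three rows carry equivalent notes.

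**The concern.** The table is where a programmer would look for the date limits, and its rule takes the earliest of the listed dates. If end of treatment falls on or near the day of last intake, it always comes first and the 28-day limb never operates. On-treatment counts would then differ according to whether the table or the SAP text was programmed. For completers the events at stake are those in the 28 days after Visit 10, which is the period that Visit 11 reviews for adverse events.

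**Working it through.** The plan states no figure for this, so the check compares the two rules in days.

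**Inputs.** Treatment lasts 52 weeks (364 days). Open-label drug starts at week 12 (day 84). The residual period is 28 days. The last dose is given at Visit 10, which protocol 6.2.2 labels the end-of-treatment visit. Early stoppers are asked to attend an early end-of-treatment visit promptly after last intake (protocol 6.2.3). Visit 11 is 28 days post-treatment (protocol 6.1). The lag k from last intake to the early visit is not given, so it is an assumption.

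**SAP text.** SAP 6.1 excludes the last day of each period. Last intake + 1 day up to last intake + 29 days (excluded) is therefore 28 days. In the blinded period it stops sooner if open-label drug starts.

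**Table rule.** The end date is min(last intake + 28, end of treatment), with first open-label intake also in the minimum for the blinded row. The result depends on what end of treatment means.

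*Reading A: the end-of-treatment visit, as in the protocol.*

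- Completer: end of treatment = day of last intake = 364, so min(392, 364) = 364. That covers 0 days after last intake, against 28 in the text.
  - Overall window: 364 + 28 = 392 days, and 28/392 = 7.1% is lost.
  - Open-label window: (364 − 84) + 28 = 308 days, and 28/308 = 9.1% is lost.
  - The 7-day repeat covers 7 days after last intake against 0 for the main analysis, so the supposedly narrower analysis is the wider one.
- Early stopper: days lost = max(0, 28 − k). This is 28 for k = 0, 21 for k = 7, 14 for k = 14 and 0 for k ≥ 28. A percentage would also need an assumed stop week, so none is given.
- Blinded row, patient going straight to open-label drug: with last blinded intake on day 83 and open-label start on day 84, the text gives 0 days after last blinded intake and the table 1. This is no material difference. Only patients who stop blinded drug and do not go straight to open-label drug are affected, by max(0, 28 − k) days.
- Between-period liver row: it pairs a bilirubin rise with an AST/ALT rise within 30 days of each other but in different periods. Taking the periods as blinded and open-label, both values lie between about day 84 − 30 = 54 and day 84 + 30 = 114. A cap at day 364 cannot remove such a pair. It can matter only for a patient who stops open-label drug within about 30 days of starting it.

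*Reading B: the end of the whole period, including post-treatment.* SAP 6.1 introduces an "open-label treatment period (with sub-periods off-treatment, post-treatment and follow-up". On that basis the cap falls at the end of the 28 days and nothing is lost. Against this, the same section ends the open-label treatment period itself one day after last intake, before post-treatment begins.

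*Reading C: a slip for end of trial.* Visit 11 is 28 days post-treatment, so completers lose about 0 days.

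**Which data are affected.** Protocol 6.2.3 describes Visit 11 as a review of adverse events and concomitant therapy, a urine pregnancy test where applicable, and an ECG and physical examination if abnormal at Visit 10. It lists no safety blood draw. For completers, only unscheduled blood samples (allowed by protocol 5.3.3) could fall in the disputed days. The effect is therefore mainly on adverse events.

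**The case against.** The strongest reply is that the intent is clear and the phrase is only loose. The 28-day rule appears in SAP 6.1, SAP 7.8.1 and two protocol sections, and the notes in the four rows repeat it. Where SAP 6.1 means the early visit, it uses the word visit. Reading A makes the 28-day limb idle for completers and turns the 7-day repeat upside down, which suggests that it was not meant. The footnote to the End date column is not visible and may define the term.

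Much of this stands. It shows that 28 days is intended, and the unseen footnote cannot be counted as missing from the plan. It does not make the end-date cells say what is intended. The protocol's usage points to reading A, and readings B and C each need something that the cells do not state.

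A reader might go further and infer that the plan definitely discards the residual period, that laboratory and liver results are cut in the same proportion, or that the arms would be compared unfairly. The documents do not support this. The term is undefined in the visible text, completers have no safety blood draw described at Visit 11, and the liver row covers only pairs around the week-12 switch. Patients who roll over lose essentially nothing in the blinded row.

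**Conclusion.** The four rows contain a limit that the SAP text does not, resting on a term with no visible definition. Under the protocol's usage the limit conflicts with SAP 6.1 for all safety data, and with SAP 7.8.1 and protocol 5.3.7 and 7.3.4 for adverse events. The size for completers runs from about 0 days (readings B and C) to 28 days (reading A). The percentages are shares of calendar days, not of events, and no percentage is claimed for the liver row. The early-stopper figures depend on the assumed lag k. Safety analyses are descriptive without hypothesis tests, and no efficacy result depends on these rows. The severity is minor: an ambiguity to settle before the safety tables are programmed.

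**What to change.** Delete the end-of-treatment limit from the four rows. The open-label, overall and between-period liver windows then end at last intake + 28 days, and the blinded window ends at the same point or at first open-label intake, if earlier. All four rows then match SAP 6.1, and the adverse event window matches SAP 7.8.1 and the protocol. If the footnote to the End date column defines end of treatment, make that definition consistent with the SAP 6.1 rule instead. The cost is the wording of four table cells, with no new data and no protocol change.

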6.2 IMPORTANT PROTOCOL VIOLATIONS

The following table defines the different categories of important protocol violations. The final column describes which protocol violations will be used to exclude patients from which analysis set(s).

Table 6.2: 1 Important protocol violations (IPVs)

Category / Code	Description	Requirements / Classification	Excluded from
A	Entrance criteria not met		
A1.1	Age < 40 years at Visit 1	Inclusion criterion 2 not met as specified in the protocol. Automatic IPV	None
A1.2	No clinical diagnosis of IPF within the last 3 years from Visit 0, based upon the ATS/ERS/JRS/ALAT 2011 guideline	Inclusion criterion 3 not met as specified in the protocol. Automatic IPV	None
A1.3	No chest high resolution computed tomography (HRCT) scan performed within 18 months of Visit 0	Inclusion criterion 4 not met as specified in the protocol. Automatic IPV	None
A1.4	Combination of HRCT pattern and surgical lung biopsy pattern (the latter if available) as assessed by central review is not consistent with the diagnosis of IPF	Inclusion criterion 5 not met as specified in the protocol. Automatic IPV	None
A1.5	FVC < 80% of predicted normal at visit 1	Inclusion criterion 6 not met as specified in the protocol but it was agreed during MQRM to only flag patients with $FVC \leq 0.79$ Automatic IPV	None
A2.1	ALT, AST, Total bilirubin > 1.5 fold upper limit of normal (ULN) at Visit 1	Exclusion criteria 1 or 2 met as specified in the protocol Automatic IPV	None
A2.2	Underlying chronic liver disease (Child Pugh A, B or C hepatic impairment)	Exclusion criterion 3 met as specified in the protocol Automatic IPV	None
A2.3	Relevant airways obstruction [i.e. pre-bronchodilator FEV1/FVC < 0.70 (i.e. 70%) at Visit 1]	Exclusion criterion 4 met as specified in the protocol but it was agreed during MQRM to only flag patients with $FEV1/FVC \leq 0.65$ Automatic IPV	None
A2.4	History of myocardial infarction within 6 months of visit 1 or unstable angina within 1 month of Visit 1	Exclusion criterion 5 met as specified in the protocol (for more details refer to the protocol) Automatic IPV	None
A2.5	Bleeding Risk	Exclusion criterion 6 met as specified in the protocol Automatic IPV	None
A2.6	Planned major surgery during the trial participation, including lung transplantation, major abdominal or major intestinal surgery	Exclusion criterion 7 met as specified in the protocol Automatic IPV	None
A2.7	History of thrombotic event (including stroke and transient ischemic attack) within 12 months of Visit 1	Exclusion criterion 8 met as specified in the protocol Automatic IPV	None

Table 6.2: 1 (continued) Important protocol violations (IPVs)

Category / Code	Description	Requirements / Classification	Excluded from
A2.8	Creatinine clearance < 30 mL/min calculated by Cockcroft–Gault formula at Visit 1	Exclusion criterion 9 met as specified in the protocol Automatic IPV	None
A2.9	Treatment with Nintedanib, pirfenidone, azathioprine, cyclophosphamide, cyclosporine, any other investigational drug, n-acetylcysteine, prednisone/prednisolone >15 mg daily or >30 mg every 2 days OR use of other systemic corticosteroids as well as any investigational drugs within 4 weeks of Visit 2	Exclusion criterion 10 met as specified in the protocol Automatic IPV	None
A2.10	Known hypersensitivity to nintedanib, peanut, soya or to any other components of the study medication	Exclusion criterion 11 met as specified in the protocol Automatic IPV	None
A2.11	Prior discontinuation of nintedanib treatment due to intolerability/ adverse events considered drug related	Exclusion criterion 12 met as specified in the protocol Automatic IPV	None
A2.12	A disease or condition which in the opinion of the investigator may interfere with testing procedures or put the patient at risk when participating in this trial	Exclusion criterion 13 met as specified in the protocol Automatic IPV	None
A2.13	Alcohol or drug abuse which in the opinion of the treating physician would interfere with the treatment and would affect patient's ability to participate in this trial	Exclusion criterion 14 met as specified in the protocol Automatic IPV	None
A2.14	Inability to understand and follow any study procedures such as but not limited to home spirometry, including completion of self-administered questionnaires without help	Exclusion criterion 15 met as specified in the protocol Automatic IPV	None
A2.15	Women who are pregnant, nursing, or who plan to become pregnant while in the trial, or not willing or able to use highly effective methods of birth control	Exclusion criteria 16 and/or 17 met as specified in the protocol Automatic IPV	None
A2.16	Acute IPF exacerbation or any respiratory tract infection in the four weeks prior to Visit 1 or during the screening period.	Exclusion criterion 18 met as specified in the protocol Automatic IPV	None
A2.17	Participation in another trial with investigational drug/s within one month prior to Visit 1 or previous enrollment in this trial	Exclusion criterion 19 met as specified in the protocol Automatic IPV	None

Table 6.2: 1 (continued) Important protocol violations (IPVs)

Category / Code	Description	Requirements / Classification	Excluded from
B	Informed consent		
B1	Informed consent not available/not done	Inclusion criterion 1 not met as specified in the protocol. Automatic IPV	All
B2	Informed consent too late	Inclusion criterion 1 not met as specified in the protocol. Medical review during MQRM, BRPM or DBLM	None
B3	Informed consent not given for pharmacogenetics samples (unspecified part) but blood sample drawn for testing	According to pharmacogenetics database and CRF Automatic IPV	None
B4	Informed consent for pharmacogenetics samples (unspecified part) too late but blood sample drawn for testing	Medical review during MQRM, BRPM or DBLM	None
B5	Informed consent not given for serum banking samples (unspecified part) but blood sample drawn for testing	According to serum banking database and CRF Automatic IPV	None
B6	Informed consent for serum banking samples (unspecified part) too late but blood sample drawn for testing	Medical review during MQRM, BRPM or DBLM	None
C	Trial medication and randomisation		
C1	Incorrect trial medication taken	Wrong medication number use at any time (after Visit 2) during the trial. IPV only if medication error leads to an actual treatment switch (will be determined after unblinding). Medical review of MQRM listings	None
C2	Randomisation not followed	Wrong medication number given leading to the patient taking treatment different from the one randomized by IXRS at time of randomisation (Visit 2). IPV only if medication error leads to an actual treatment switch. (will be determined after unblinding). Medical review of MQRM listings	None
C3	Overall Compliance not between 80% and 120% inclusive	Medical review during MQRM	None
C4	Medication code broken inappropriately	Except for emergency situation. Medical review of MQRM listings	None
C5	Drug not permanently discontinued despite criteria of Section 3.3.4.1 of CTP met	Medical review of MQRM listings	None
D	Concomitant medication		
D1	Patient received prohibited concomitant therapies during treatment phase	Medical review of MQRM listings	None

Table 6.2: 1 (continued) Important protocol violations (IPVs)

Category / Code	Description	Requirements / Classification	Excluded from
E	Missing data		
E1	No post-baseline blood CRPM assessments up to Week 12	Automatic IPV	None
F	Incorrect timing		

¹Time deviations will only be flagged as important PV, when leading to exclusion of the entire subject from an analysis set
Source: BI reference document ‘Protocol Violation Handling Definitions’ (001-MCS-50-413_RD-01) (2)

For analyses defined in this section, the blinded and open-label period will be analyzed separately and additionally, a pooled analysis across both periods will be performed but including displays by randomized treatment.

